Women randomized to CSC will receive a telephone counseling call during which the opportunity to complete CRC screening (FOBT or a colonoscopy) and/or mammography will be offered. The CSC will include tailored counseling as well as the ability to schedule BC and CRC screening tests. The combined TIWeb + CSC group will receive a mailed TIWeb followed in four weeks by a CSC with the same opportunity to receive FOBT kits or schedule a colonoscopy and/or mammogram. The nurse counselor, knowing the participant is a good candidate for screening tests, will be trained to schedule CRC or BC screening appointments or to mail FOBT kits to individuals in the intervention groups even if they have not had a recent clinic visit. The usual care group will receive usual care that varies dependent upon the practice setting. Participants will have a baseline telephone or electronic survey prior to randomization that assesses beliefs, knowledge, self-reported CRC & BC screening, and other study variables. Four weeks following intervention, participants will be surveyed via

telephone or electronic survey on CRC & BC beliefs, knowledge, and participant involvement in and satisfaction with the intervention. Again at 6 months, a final telephone or electronic survey will be done and claims data collected. (See Figure 2) A Community Advisory Board will be involved in design and review of interventions, accrual, and intervention delivery.

In order to tell whether or not the two week opt out period is sufficient time for women to opt out, the PI and project manager will monitor a spreadsheet that will be developed for tracking calls made by study staff to women who indicate that they did opt out of the study by returning the refusal postcard, calling the toll free number, or emailing the project manager. If a woman indicates that she did opt out the study staff will apologize and indicate to the project manager or PI that this has happened. The project manager will then make sure her documentation is destroyed. Once this occurrence has happened a total of ten times, the PI will reevaluate the opt out time period and consider revising. Any occurrences will be reported to the IRB at continuing review.

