¹²⁸⁾ and consistent with our previous research.^(9, 10) Construct validation for these stage measures was established via principal components analyses in an original and a replication study (involving 142 and 676 women, respectively).^(119, 128) Items for CRC and BC screening will determine whether participants: 1) have ever had a mammogram, FOBT, sigmoidoscopy, or colonoscopy; 2) have thought about having a mammogram, FOBT, sigmoidoscopy, or colonoscopy; or 3) intend to have any of these tests in the next six months. We will also ask participants if CRC or BC screening tests were for screening or diagnostic purposes and use their responses as a covariate. Screening and diagnostic procedures have different CPT codes.

Mammography and colonoscopy scheduling will be based on the location of the participating physician. The study team will be given a preferred list of sites to be scheduled as well as alternative sites if the patient chooses. Results of screenings will be sent immediately to the participant's primary health care provider as part of her routine care.

Past Screening History will be measured by self-reported items that assess CRC and BC screening tests women have had in the past 20 years or since the individual turned 50. Self-report will be the most feasible method to assess screening history since claims data may not accurately reflect all screening tests done in other health care settings or while they were covered by a different health insurance plan.

Participant Involvement: will be measured for the TIWeb and for the CSC. The participant involvement scale for TIWeb has 19 items that address interest and engagement in the program and its content. The items, piloted with 36 people (see Preliminary Studies), address ease of use, relevancy, information content, barriers, and general satisfaction. The Cronbach's alpha was 0.89 and 100% of people indicated that they found the program interesting, easy to use, easy to understand, and containing information that was important to them. The survey instrument can be found in **Appendix E**. There are 15 items that measure participant involvement in the CSC. Participants will be called within 4 weeks following intervention to obtain data on involvement with the intervention.

Beliefs about CRC or BC Screening

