data collection using computer-assisted telephone interviewing. Following this initial demonstration, interviewers will role-play with videotaped feedback until they have reached 100% compliance with guidelines for data collection integrity. Research assistants who provide technical assistance to women needing help to use the TIWeb in their homes will be trained to assist with use of the TIWeb without providing additional education or information. They will practice and role-play until they have reached 100% compliance with guidelines for intervention delivery.

Quality Assurance for Intervention Delivery

Quality assurance and monitoring for integrity of intervention delivery are described in the previous section and in the Process Evaluation section of the proposal. Procedures for monitoring outcome data collection are described below. [name] will be responsible for oversight of monitoring quality assurance for intervention delivery, outcome data collection, and technical support.

Quality Assurance for Outcome Data Collection

After data collection begins, data collectors/interviewers will be part of the biweekly research team meetings that include the investigators, project managers, and research assistants to discuss project implementation and address questions or concerns that have arisen in the previous two weeks. All interviewers will be required to record one telephone interview each month; these interviews will be reviewed by the project manager and the investigators for quality assurance purposes. An evaluation checklist has been developed to assess the quality of data collection interviews and adherence to study protocol. Interviewers will be trained to query participants who have reported an abnormal mammogram to ensure prompt medical follow-up.

Quality Assurance for Data Managers

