Data management will be handled by biostatisticians in the Indiana University, School of Medicine, Department of Medicine, Division of Biostatistics. Data monitoring will occur weekly as data from each interviewer are merged with the larger data set. Biostatisticians will handle all data merging. Backup data files will be kept in the Principal Investigator's office as well as the office of the biostatisticians. Interviewers will complete a form each week when sending data to be merged. The form will alert the biostatisticians to any abnormalities in the data set. All computers that will be used to collect and send data during implementation of the study or to store data at the central secured location will be password-protected.

Data integrity and security

IUPUI-Clarian Institutional Review Board approvals and related documents as well as all signed informed consent forms will be kept at Indiana University, School of Nursing in a locked location. All computers will be password-protected. Only trained grant personnel will have access to data. Once all data have been linked together for individuals, identifiers will be deleted from the data base that includes interview and mammography data. Identifiers will be kept in separate locked files from the collected data and used only for follow-up data collection. At the end of the study all identifiers will be deleted.

Identification of Adverse Effects

The principal investigators will monitor adverse events. First, adverse events will be monitored through the interviewers. Any concern will be brought to the attention of the principal investigators and, if immediate action is necessary, it will be undertaken and later discussed at team meetings. Adverse events will also be immediately reported to the IUPUI-Clarian Institutional Review Board. Participants will have a phone number to call if problems occur. Indiana University has a process in place whereby random monitoring for data integrity will occur by a committee external to the grant staff.

Data Sharing Plan

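### The interviewer query on follow-up of an abnormal result names mammograms only; extend it to colorectal tests, chiefly a positive FOBT or FIT

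*Combined protocol and SAP*

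**What the plan says.** The instruction is in Section E, under Quality Assurance for Outcome Data Collection: "Interviewers will be trained to query participants who have reported an abnormal mammogram to ensure prompt medical follow-up".

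Other parts of the document bear on the same point:

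- **What the surveys ask.** Under D.11 Measurement, the items establish whether participants "have ever had a mammogram, FOBT, sigmoidoscopy, or colonoscopy", and whether they have considered or intend these tests. D.11 adds: "We will also ask participants if CRC or BC screening tests were for screening or diagnostic purposes".
- **Where results go.** D.11 also states: "Results of screenings will be sent immediately to the participant's primary health care provider as part of her routine care". This is not limited to mammograms.
- **General escalation.** Section E, Identification of Adverse Effects, says: "Any concern will be brought to the attention of the principal investigators and, if immediate action is necessary, it will be undertaken". It also says: "Participants will have a phone number to call if problems occur".
- **What the study supplies.** D.1 has the nurse counselor trained to schedule appointments or to "mail FOBT kits to individuals in the intervention groups even if they have not had a recent clinic visit".
- **Survey mode.** D.1 states: "Again at 6 months, a final telephone or electronic survey will be done and claims data collected". D.4 and D.9 likewise allow either mode, while D.8 speaks of calls at 4 weeks and 6 months.

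**The concern.** The one targeted safety question is attached to breast screening, while the trial mainly promotes colorectal screening. An interviewer who is told of an abnormal mammogram has been trained to ask about follow-up. An interviewer who is told of a positive FOBT may raise it as a concern, but nothing tells her to ask whether follow-up was arranged.

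A positive FOBT or FIT is the case that matters most, because it leads nowhere unless someone acts on it, and some kits will go to women with no recent clinic visit. Endoscopy is a narrower case, since B.1 notes that polyps can be removed during the examination.

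What is at stake is participant safety. No efficacy estimate depends on this sentence.

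**Working it through.** The check is mainly a comparison of text. The plan states no figure on this point, so there is none to reproduce.

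**1. Is there a matching query elsewhere?** I looked at each place that describes results, abnormal findings, survey mode and adverse events. Section E's mammogram query is the only instruction to ask a participant about follow-up of an abnormal result. The other mention of abnormality, under Quality Assurance for Data Managers, concerns the data set.

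**2. Do the other safeguards do the same job?** The provider route in D.11 covers colorectal tests, but it is not a question to the participant and does not confirm that follow-up took place. Escalation to the principal investigators covers any concern, but depends on the interviewer recognising one. The biweekly team meetings can take up such a report once somebody raises it. All three apply equally to mammograms, and the sponsor still added a direct query for mammograms. The documents give no reason for treating colorectal tests differently.

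**3. Which tests does the trial generate?** Section A makes nonadherence to CRC screening a condition for all women and CRC adherence the primary outcome. From the D.12 table, Group A (already up to date on mammography) is planned at 119 per arm, so 4 × 119 = 476 of 1,588 women. Their tailored program aims at CRC screening, although D.8 also gives all women a yearly mammography message.

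**4. Scale.** Inputs from the D.12 table: 357 evaluable women in each of four arms, with planned 6-month CRC adherence of 20%, 30%, 40% and 55%.

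- Evaluable women: 4 × 357 = 1,428.
- Women with a colorectal test: 357 × (0.20 + 0.30 + 0.40 + 0.55) = 357 × 1.45 = 517.65, about 518.

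This counts tests, not abnormal results. The documents give neither an abnormal-result rate nor the split between FOBT and colonoscopy, so the number of women affected cannot be derived.

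**5. Could the extra query disturb the outcomes?** Table 6 counts any listed test since the intervention as adherence to any CRC screening. A woman with a positive FOBT is therefore already adherent, and a later colonoscopy changes nothing on that outcome. D.13 makes the two CRC outcomes identical for average-risk women. Only a woman with a family history, for whom Table 6 requires colonoscopy, could change status on risk-appropriate adherence.

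Queries would follow uptake. If test mix and abnormal-result rates are the same in all arms (an assumption), the combined arm would have 0.55 / 0.20 = 2.75 times as many queries as usual care.

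**The case against.** The strongest reply is that this is a redundant check. Results already reach the provider at once, concerns go to the principal investigators, participants have a number to call, and the team meets every two weeks. That stands, and it limits the point to a modest one. A reader might infer that abnormal colorectal results would go unfollowed. The documents do not support that.

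A reader might also infer that women who answer online fall outside the query. The text does not establish this. The instruction refers to women who have reported an abnormal mammogram, without saying by which mode. The same survey center collects data in both modes, so an interviewer could query a woman who reported online. The text describes no electronic flag, but the survey forms are in appendices that are not available here and may contain one. The electronic route is therefore something to confirm, not a demonstrated defect.

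It is tempting to express the gap as a proportion of tests or of survey modes covered. Such ratios do not measure harm. The D.11 items, as described, ask about having, considering or intending a test, not about its result. The interventions offer only FOBT or colonoscopy, so sigmoidoscopy should not carry equal weight. The mode count rests on the unsupported reading just described.

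Finally, the extra contact would be unequal across arms. That is correct and belongs in the cost, but it reaches only risk-appropriate adherence in women with a family history.

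**Conclusion.** The point holds as a gap in the wording of a safety instruction. As written, a woman who reports a positive FOBT does not get the follow-up question that the sponsor chose to provide for an abnormal mammogram, in a trial whose primary outcome is CRC screening.

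It is a cheap improvement to consider, not a failure of participant protection. Its size in affected women is unknown. It does not touch sample size, power, the type I error rate or the any-CRC-test outcome.

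The conclusion assumes that the appendix forms contain no such query for colorectal tests. If they do, the change only brings the protocol text into line with them. The narrow wording may be a carry-over: nearby text in Section E also refers to mammography records alone and still gives 2,616 participants, against 1,588 in D.3. That is an inference, but nothing presents the mammogram-only query as deliberate.

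**What to change.** In Section E, Quality Assurance for Outcome Data Collection, replace *an abnormal mammogram* with *an abnormal mammogram or colorectal screening test (chiefly a positive FOBT/FIT)*. Apply it in the same way in all four arms. Clinical content and timing of follow-up stay with the investigators and treating providers.

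Then check the existing survey forms, including the electronic version, to see that such a report would reach an interviewer. Change the forms only if it would not.

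The cost is one sentence, a check of the forms, a short IRB amendment and a few extra queries. More queries would fall in arms with higher uptake. A query at 4 weeks could prompt a colonoscopy that then counts as risk-appropriate adherence in a woman with a family history. The effect should be small and should be acknowledged when that outcome is reported.
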